**NCT#: NCT04061044**

**DATE: JULY 11, 2019**

Study Title	A Prospective, Multicenter, Open Label Extension Study to Evaluate the Long Term Safety of OTX-TP (sustained release travoprost) Intracanalicular Insert
Test Article	OTX-TP (sustained release travoprost) Intracanalicular Insert
Phase of Clinical Study	3
Study Objective	To evaluate the long term safety of repeat dose OTX-TP, a sustained release travoprost drug product, placed in the canaliculus of the eyelid in the treatment of subjects with open-angle glaucoma or ocular hypertension.
Product Description	
The OTX-TP drug product is a dried polyethylene glycol (PEG) based, rod-shaped hydrogel intracanalicular insert designed to be placed in the superior or inferior canaliculus. The hydrogel swells on contact with moisture to occlude the lumen, thus holding the intracanalicular insert in place. Once OTX-TP swells to fill the canaliculus, it is contained in the canaliculus until the hydrogel is resorbed.
 
[REDACTED]
 
[REDACTED]
 
[REDACTED]
 
The intracanalicular insert also has an inert PEG tip to aid in insertion.
 
Travoprost is a synthetic prostaglandin F2<math>\alpha</math> analogue used for reducing elevated intraocular pressure in subjects with open-angle glaucoma or ocular hypertension. Travoprost is the active pharmaceutical ingredient in Travatan®, Travatan Z® and IzbaTM (Alcon Laboratories Inc., Fort Worth, TX) which have been approved by the US FDA for this indication.
 
OTX-TP is an extended release drug delivery insert designed to release travoprost over a period of up to 12 weeks.
 
As both the hydrogel [REDACTED] degrade by hydrolysis, OTX-TP softens, liquefies and is cleared through the nasolacrimal duct.

Study Design and Overview	Study Design: This is a prospective, multicenter, open label trial, to evaluate the long term safety of OTX-TP, a sustained release drug product placed in the canaliculus of the eye in subjects with open-angle glaucoma or ocular hypertension. A total of up to 100 subjects (200 eyes) who have completed the OTX-16-002 trial, A Prospective, Multicenter, Randomized, Parallel-Arm, Double Masked, Vehicle Controlled Phase 3a Study Evaluating the Safety and Efficacy of OTX-TP in the Treatment of Subjects with Open-Angle Glaucoma or Ocular

	
Hypertension, will receive OTX-TP in this trial to evaluate the long term safety of the OTX-TP drug product and will be followed for approximately 12 months.
 
The study will be conducted at up to 15 qualified investigative sites in the United States.
 
Study arms and treatments:
 
OTX-TP: In the OTX-16-002 trial, subjects were randomized to receive either OTX-TP or a placebo vehicle. In this long term safety study, all subjects will receive OTX-TP in both eyes. Masking from the OTX-16-002 will remain in place until all data review has been completed.


Study Duration and Study Visits
	
Each subject's participation in the study is intended to last for approximately 12 months.
 
Once a subject has successfully completed OTX-16-002, and has provided written informed consent, the subject will be screened for entry into this open label extension trial. Visit 1 is a screening and insertion visit that should take place within 7 days from when the subject exits the OTX-16-002 trial. This visit may be conducted on two separate days. At the end of Visit 1, subjects will have the OTX-TP intracanalicular insert placed in both eyes.
 
Subjects in this study will not be randomized. All subjects will receive OTX-TP in both eyes. Subjects will be followed every 6 weeks during this study for approximately 12 months.
 
All subjects will undergo follow-up visits at 1.5 months (Visit 2), 3 months (Visit 3), 4.5 months (Visit 4), 6 months (Visit 5), 7.5 months (Visit 6), 9 months (Visit 7), 10.5 months (Visit 8), and 12 months (Visit 9). If at any visit, the investigator deems it necessary to initiate IOP-lowering drops as rescue therapy due to an increase in IOP, the subject will begin the IOP-lowering drops at the Investigator's discretion and continue to be followed until the intracanalicular insert is no longer present and patency is confirmed.
 
Tear fluid samples will be collected at specified study visits, if possible. At visits where no insertion is required, tear fluid samples should be collected following the visualization assessment. At visits requiring an insertion, tear fluid samples should be collected approximately an hour prior to insertion, and again up to two hours post insertion.
 
Insertions will be attempted at 3 months (Visit 3), 6 months (Visit 5), and 9 months (Visit 7). Insert placement is to be performed after patency confirmation only if prior insert is not present, whether or not IOP is controlled. If IOP is controlled and insert is present, insertion may be deferred until the next study visit. If IOP is not controlled and insert is present, the insert will be removed and another insert will be placed.

	
If insertion is not successful at any visit, re-embedments may be attempted at the Investigator's discretion within seven days of the failed attempt. If insertion is again unsuccessful, sites should discuss potential for re-embedding with Ocular Therapeutix on a case by case basis.
 
For subjects with Early Loss of Intracanalicular Insert:
 
At any visit, including unscheduled visits, prior to the scheduled replacement visits (3 months, 6 months, and 9 months), if the intracanalicular insert is not visualized in one or both eyes by the Investigator, the Investigator will insert a new intracanalicular insert in the respective eye(s) after confirming patency. For any insert replacements, IOP assessments should be completed prior to replacement. The subject will continue to return for follow-up visits per the study schedule. The number of replacements will be tracked and documented on the appropriate Case Report Form (CRF).

Inclusion Criteria	
Subjects must meet all of the following criteria to be eligible:
 
 
- Had prior bilateral treatment and completion, through a minimum of week 12, of the OTX-16-002 trial
 
- Are informed of the nature of the study and subject is able to comply with study requirements and visit schedule for one year
 
- Have provided written informed consent, approved by the appropriate Institutional Review Board
 

Exclusion Criteria	
Subjects who meet any of the following criteria are not eligible:
 
 
- Had more than 1 replacement, per eye, during participation in the OTX-16-002 trial
 
- Had punctal or canalicular related adverse events during the OTX-16-002 trial which required discontinuation (e.g., canalicularitis)
 
- Used prohibited medications during the OTX-16-002 study, or the period between OTX-16-002 and this trial (with the exception of short term medication used to treat an adverse event or rescue therapy)
 
- Missed more than 2 visits during participation in the OTX-16-002 trial
 
- Had IOP <math>\geq</math> 34 mmHg at the Screening/Insertion Visit, or any visit during the OTX-16-002 trial
 
- Require contact lens use at any point during the study including the Screening/Insertion Visit(s)
 
- Have planned intraocular surgery or laser over the one year study period
 
- Have a cup to disc ratio <math>> 0.80</math> (horizontal or vertical measurement) in either eye
 
- Are currently pregnant or breast-feeding or who wishes to become pregnant during the length of study participation
 

	
 
- Are determined by the Investigator to be ineligible for reasons not already specified (e.g., systemic or other ocular disease/abnormality, not a candidate for topical prostaglandin, therapy, specifically travoprost) if the health of the subject or the validity of the study outcomes may be compromised by the subject's enrollment
 
- Are an employee of the site that is directly involved in the management, administration, or support of the study, or are an immediate family member of the same.
 
- Are participating or plan to participate in any other investigational drug or device study during this study
 

Pharmacokinetics Parameters	
The following pharmacokinetic parameters will be analyzed from tear fluid samples collected from subjects:
 
The pharmacokinetic profile of travoprost and travoprost acid concentrations in tear fluid versus time.
 
The maximum (<math>C_{max}</math>) and minimum (<math>C_{min}</math>) concentration of travoprost and travoprost acid in tear fluid.
 
Calculations will be completed by the PK lab for tear fluid analysis.

Safety Evaluations	
Safety evaluations include:
 
 
- Adverse events
 
- Subject ocular comfort assessment
 
- Best corrected visual acuity (BCVA)
 
- Slit lamp biomicroscopy including assessment and grade of ocular hyperemia (at slit lamp) and punctum exam
 
- Intraocular pressure (IOP)
 
- Fundus examination
 
- Optical Coherence Tomography of optic nerve on nerve fiber layer
 
- Automated perimetry
 
- Number of subjects who need rescue therapy over the study period
 

Exploratory Evaluations	
 
- Visualization of intracanalicular insert by the Investigator at each time point
 
- Ease of placement of intracanalicular insert
 
- Number of intracanalicular inserts required in each eye for the study period per subject
 

Procedural Exclusion Criteria	
Unsuccessful punctal dilation of either eye (if needed) or punctum of either eye is too small to allow transient dilation to 0.7 mm prior for insertion of OTX-TP.

## **STATISTICAL ANALYSIS**

### **Study Populations**

Safety: The Safety population will include all subjects who receive any investigational study medication (OTX-TP).

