### **Unit of Analysis**

The unit of analysis in this study will be any eye that received any investigation study medication. Summaries will be completed including all treated eyes.

Ocular (occurring in any treated eye) and non-ocular adverse events will be presented at the subject level.

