### **Demographics and Baseline Data**

Subject demographics: gender, ethnicity, race, age category (< 65 years and  $\geq$  65 years), and iris color will be presented using discrete summary statistics. Age will also be presented using continuous summary statistics.

Non-ocular and ocular medical history will be summarized by treatment group using discrete summaries.

Subject disposition will be presented, including the number of subjects screened, enrolled and treated. The number of subjects who completed the study and reasons for discontinuation will be summarized.

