### **Safety Analyses**

The primary safety analysis will summarize treatment emergent ocular AEs (TEAE) using discrete summaries at the subject (occurring in any treated eye) and event level by system organ class and preferred term for each treatment group. A TEAE will be defined as occurring after initiation of treatment with OTX-TP this open label extension study.

Treatment emergent non-ocular AEs will be summarized using discrete summaries at the subject and event level by system organ class and preferred term for each treatment group. Treatment related treatment emergent ocular and non-ocular AEs and serious treatment emergent adverse events will be summarized similarly. Treatment emergent ocular and non-ocular AEs will also be summarized by severity. Adverse events will be coded using the Medical Dictionary for Regulatory Activities (MedDRA) by system organ class and preferred term.

Intraocular pressure data will be summarized using continuous summaries, including change from baseline.

Slit lamp biomicroscopy and dilated fundoscopy measures will be summarized using discrete summary statistics.

Visual acuity data will be summarized using both continuous summaries, including change from baseline, and discrete summaries, including change from baseline in the number of lines and the proportion of subjects with a worsening of  $\geq$  3 lines from baseline.

Ocular hyperemia will be summarized using discrete summary statistics.

Ocular comfort will be summarized using continuous summary statistics.

Optical Coherence Tomography of Optic Nerve on Nerve Fiber Layer data will be summarized using continuous and discrete summary statistics, including change from baseline, as appropriate.

Summaries of other safety related outcomes will be provided.

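### Does limiting the ocular adverse event table to treated eyes lose events from failed insert placements?

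*SAP*

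**What the plan says.** Four statements in the SAP set the scope of the ocular safety output.

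- Study Populations: "The Safety population will include all subjects who receive any investigational study medication (OTX-TP"). No other population is defined.
- Unit of Analysis: "The unit of analysis in this study will be any eye that received any investigation study medication". The same section adds: "Ocular (occurring in any treated eye) and non-ocular adverse events will be presented at the subject level".
- Safety Analyses, primary analysis: "The primary safety analysis will summarize treatment emergent ocular AEs (TEAE) using discrete summaries at the subject (occurring in any treated eye"), and also at event level.
- Safety Analyses, time window: "A TEAE will be defined as occurring after initiation of treatment with OTX-TP this open label extension study".

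Two further lines bear on subjects or eyes that were not treated. Demographics and Baseline Data states "Subject disposition will be presented, including the number of subjects screened, enrolled and treated". Safety Analyses closes with "Summaries of other safety related outcomes will be provided".

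The protocol plans an insert in both eyes of every subject but allows for failure. Study Duration and Study Visits permits another attempt within seven days of an unsuccessful insertion, with later attempts discussed case by case with the sponsor. Procedural Exclusion Criteria excludes a subject if punctal dilation fails in either eye.

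**The concern.** The product is placed in the canaliculus, so dilation and insertion are part of giving it. A failed placement is one setting in which punctal or canalicular injury would be looked for. Read literally, the SAP drops an eye from the primary table because the procedure failed.

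The sharpest case is a subject with one treated eye and one eye in which insertion never succeeds. That subject is in the Safety population. An ocular event in the untreated eye is neither an ocular event in a treated eye nor a non-ocular event, so it belongs to neither class that the SAP presents.

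The start of the time window raises a second question. If treatment starts when the insert is in place, an event from the first dilation, or from a failed first attempt, has its onset too early to count. If it starts with the procedure, the same event counts. Two programmers could therefore build different primary tables.

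**Working it through.** **The plan's own figure.** Determination of Sample Size uses n = 100 and a true subject rate of 3%.

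- P(at least one event) = 1 − 0.97^100 = 0.9524, which meets the stated 95%.
- With zero events, the one-sided 95% upper bound is 1 − 0.05^(1/100) = 2.95%, below the stated 3%.

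Both reproduce. The statement concerns treated subjects, so the handling of untreated eyes leaves it as it is.

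**Which eyes can fall through.** There are three possible routes.

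1. *Dilation fails before any insert is placed.* This is a procedural exclusion, at a visit that combines screening and insertion. Leaving such subjects out of a treated set is conventional.
2. *Insertion fails for good in both eyes.* The subject never receives OTX-TP and is outside the Safety population.
3. *Insertion fails for good in one eye and the other is treated.* The subject is in the Safety population, but the untreated eye has no stated place.

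A failed re-insertion at a later visit is in an eye that already counts as treated, so its events stay in the table. Only routes 2 and 3 remain, and both need first placement to fail after any further attempts. Inclusion Criteria requires prior bilateral treatment in OTX-16-002. Exclusion Criteria removes subjects who had more than one replacement per eye there, or punctal or canalicular events that led to discontinuation.

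**Number of eyes.** The protocol gives "A total of up to 100 subjects (200 eyes") as the maximum. It gives no failure rate, so p below is an assumed per-eye rate of final failure, with eyes taken as independent. Expected never-treated eyes = 200p, and P(at least one) = 1 − (1 − p)^200.

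| p | Expected eyes | P(at least one eye) |
|---|---|---|
| 0.1% | 0.2 | 18% |
| 0.5% | 1 | 63% |
| 1% | 2 | 87% |
| 2% | 4 | 98% |

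These are chances of a never-treated eye, not of an omitted event. A never-treated eye without an event changes nothing in the table. If an assumed 10% of such eyes have an event, replace p by 0.1p:

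| p | Expected omitted events | P(at least one omitted event) |
|---|---|---|
| 0.1% | 0.02 | 2% |
| 0.5% | 0.1 | 10% |
| 1% | 0.2 | 18% |
| 2% | 0.4 | 33% |

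**Effect of one omission.** In route 3 with 100 subjects, one omitted event lowers the subject-level rate for its term by at most 1/100 = 1.0 percentage point. It lowers it by nothing if the treated eye has the same event.

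**The time window.** The SAP does define the start: OTX-TP treatment begun in this extension. It leaves open the procedural step, and whether the start is set per eye or per subject. The step matters only for onsets before first placement, during the first procedure or between a failed attempt and a later success. Every onset in a treated eye after first placement counts on either reading.

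**The case for a change.** The best case for a change is that safety is the trial's sole objective and the remedy is cheap. One sentence would fix the start of treatment, and one listing would show events in attempted but untreated eyes. The disposition table promises counts of subjects, not their events, and the closing line on other safety outcomes permits such a listing without committing to it. Route 3 cannot be put down to screen failure, because the subject was treated.

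The route 3 point stands as a reading of the text, though it is not the only reading. The SAP does not define what it means to receive treatment, so a failed attempt might be counted. In Safety Analyses the restriction to treated eyes is attached to the subject-level count, and could simply be the rule for collapsing two eyes into one subject. Unit of Analysis supports the narrower reading more strongly, so the wording is at least ambiguous.

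The case for acting on it does not stand. The objective is the long-term safety of repeated OTX-TP, and an acute event in an eye that never received the product is at its edge. Adverse events are a listed safety evaluation in the protocol, and nothing suggests that these would go uncollected. The extra listing would be a reasonable courtesy, but it would not correct an error.

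**Conclusion.** No change follows. There is a narrow gap: on a literal reading, an ocular event in the never-treated eye of a treated subject has no stated table, and the step that starts treatment is not named. A safety set of treated subjects is standard, and it would stay as it is even if the extra listing were added. Naming the starting step is detail that analysts ordinarily settle in the programming specifications, and the SAP already leaves room for further safety summaries.

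The size cannot be calculated from the documents and is probably very small. Under the assumed failure rates of 0.1% to 2%, and an assumed 10% event rate in failed eyes, 0.02 to 0.4 events would be omitted. Each would be worth at most 1.0 percentage point on one term. These figures rest on 200 independent eyes, and the protocol gives 200 as a maximum. The SAP tests no formal hypothesis, its sample size statement reproduces, and no result or conclusion has been shown to depend on this point.

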### **Unit of Analysis**

The unit of analysis in this study will be any eye that received any investigation study medication. Summaries will be completed including all treated eyes.

Ocular (occurring in any treated eye) and non-ocular adverse events will be presented at the subject level.

### **Hypotheses**

There are no formal hypotheses to be tested in this single arm safety study.

### **Determination of Sample Size**

One-hundred (100) subjects treated for 1 year yields at least 95% probability of observing adverse events that occur at a true subject rate of 3% or greater. That is, if an adverse event of a given type is not observed in 100 subjects, then, with 95% one-sided confidence, the true rate of the adverse event will be <3%.

### **Methods of Analyses**

Summaries for continuous variables will include the sample size, mean, standard deviation, median, minimum, and maximum. Minima and maxima will be reported with the same precision as the raw values; means, standard deviations, and medians will be presented to one additional decimal place than reported in the raw values. Summaries for discrete variables will include frequencies and percentages. All percentages will be rounded to one decimal place (i.e., XX.X%).

Change from baseline will be calculated as follow-up visit minus baseline. The baseline visit will be defined as the last non-missing measure prior to initiation of OTX-TP (either in this study or in OTX-16-002), with the exception of OCT (which was not measured in OTX-16-002), for which baseline will be defined as the last non-missing measure prior to initiation of OTX-TP during this open label extension study.

All summaries will be presented where appropriate by visit, summarizing data from all subjects at a given visit in this open label extension study, regardless of whether subjects received OTX-TP in OTX-16-002. Additional analyses may be performed including the OTX-16-002 treatment data for subjects receiving OTX-TP in OTX-16-002.

Summaries will be presented by separately for subjects/eyes who received OTX-TP during OTX-16-002, subjects/eyes who received OTX-PV during OTX-16-002, and over all subjects/eyes.

### **Demographics and Baseline Data**

Subject demographics: gender, ethnicity, race, age category (< 65 years and  $\geq$  65 years), and iris color will be presented using discrete summary statistics. Age will also be presented using continuous summary statistics.

Non-ocular and ocular medical history will be summarized by treatment group using discrete summaries.

Subject disposition will be presented, including the number of subjects screened, enrolled and treated. The number of subjects who completed the study and reasons for discontinuation will be summarized.

### **Safety Analyses**

The primary safety analysis will summarize treatment emergent ocular AEs (TEAE) using discrete summaries at the subject (occurring in any treated eye) and event level by system organ class and preferred term for each treatment group. A TEAE will be defined as occurring after initiation of treatment with OTX-TP this open label extension study.

Treatment emergent non-ocular AEs will be summarized using discrete summaries at the subject and event level by system organ class and preferred term for each treatment group. Treatment related treatment emergent ocular and non-ocular AEs and serious treatment emergent adverse events will be summarized similarly. Treatment emergent ocular and non-ocular AEs will also be summarized by severity. Adverse events will be coded using the Medical Dictionary for Regulatory Activities (MedDRA) by system organ class and preferred term.

Intraocular pressure data will be summarized using continuous summaries, including change from baseline.

Slit lamp biomicroscopy and dilated fundoscopy measures will be summarized using discrete summary statistics.

Visual acuity data will be summarized using both continuous summaries, including change from baseline, and discrete summaries, including change from baseline in the number of lines and the proportion of subjects with a worsening of  $\geq$  3 lines from baseline.

Ocular hyperemia will be summarized using discrete summary statistics.

Ocular comfort will be summarized using continuous summary statistics.

Optical Coherence Tomography of Optic Nerve on Nerve Fiber Layer data will be summarized using continuous and discrete summary statistics, including change from baseline, as appropriate.

Summaries of other safety related outcomes will be provided.

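### Hyperemia, slit lamp/punctum, fundus and comfort have no planned within-eye comparison with baseline, so this single-arm safety study would not tabulate how many eyes worsen on them

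*SAP*

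**What the plan says.** The protocol's Safety Evaluations list includes ocular comfort, fundus examination, IOP, and "Slit lamp biomicroscopy including assessment and grade of ocular hyperemia (at slit lamp) and punctum exam". The SAP's Safety Analyses section handles them as follows.

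- Slit lamp and fundus: "Slit lamp biomicroscopy and dilated fundoscopy measures will be summarized using discrete summary statistics".
- Hyperemia: "Ocular hyperemia will be summarized using discrete summary statistics".
- Comfort: "Ocular comfort will be summarized using continuous summary statistics".
- IOP: "Intraocular pressure data will be summarized using continuous summaries, including change from baseline".
- Visual acuity: change from baseline, plus the proportion of subjects losing three or more lines.
- OCT: continuous and discrete summaries, with change from baseline as appropriate.

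Methods of Analyses defines a discrete summary as frequencies and percentages. It defines a continuous summary as n, mean, SD, median, minimum and maximum. Summaries are by visit in this extension where appropriate, and are split by prior OTX-TP or prior vehicle as well as pooled. Baseline is the latest available value before first OTX-TP, in whichever study that exposure began; OCT is the one exception, because OTX-16-002 did not measure it.

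The primary safety analysis is of ocular treatment-emergent adverse events (TEAEs), counted from the start of OTX-TP in this extension. On hypotheses the SAP says: "There are no formal hypotheses to be tested in this single arm safety study".

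**The concern.** Long-term safety is the sole objective and there is no concurrent control, so the natural question for each local measure is how many eyes became worse than they were before OTX-TP. Hyperemia, the punctum examination and comfort are the measures closest to an insert placed in the canaliculus.

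A frequency table gives the share of eyes with a finding at a visit. It does not separate eyes that always had the finding from eyes that acquired it, because recoveries and new cases cancel. Mean comfort scores at successive visits, with no change score, have the same limitation, and the eyes contributing can differ from visit to visit.

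At stake is whether the study report can state a number and proportion of eyes, and of subjects, that worsened on these measures. The plan provides such a statement for visual acuity.

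**Working it through.** **The plan's own figure.** Determination of Sample Size gives at least 95% probability of seeing an event with a true subject rate of 3% among 100 subjects. Check: 1 − 0.97^100 = 0.9524. With 0 events in 100, the one-sided 95% upper limit is 1 − 0.05^(1/100) = 2.95%, below 3%. The figure reproduces, and the present point neither disputes it nor depends on it.

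**What frequencies can tell us: present/absent finding.** Let p1 be the proportion of eyes with the finding at baseline and p2 the proportion at a later visit, in the same eyes. The proportion with a new finding lies between max(0, p2 − p1) and min(p2, 1 − p1). The documents give no prevalence, so p1 and p2 are assumed. The protocol's maximum of 200 eyes is used.

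| Assumed p1 = p2 | Range of new findings | Eyes out of 200 |
|---|---|---|
| 30% | 0% to 30% | 0 to 60 |
| 2% | 0% to 2% | 0 to 4 |

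**Graded finding.** Assume grade 0/1/2/3 counts of 80/80/30/10 at both baseline and a visit.

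- Minimum worsened: 0, if no eye moves.
- Maximum worse by at least one grade: an eye ending at grade 0 cannot have worsened, so the ceiling is 200 − 80 = 120 eyes (60%). It is attainable. The 80 eyes ending at grade 1 come from grade 0, the 30 ending at grade 2 and the 10 ending at grade 3 come from grade 1, and the remaining 40 + 30 + 10 = 80 eyes end at grade 0.
- Maximum worse by at least two grades: only eyes ending at grade 2 or 3 qualify, so 30 + 10 = 40 eyes (20%). It is attainable if all 40 started at grade 0.

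Identical frequency tables therefore fit anything from 0 to 120 eyes worsening.

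**Baseline and TEAE windows side by side.** For a subject previously on OTX-TP, the SAP baseline lies in OTX-16-002. The by-visit summaries cover visits in this extension, so that pre-exposure value need not appear in them. A TEAE must occur after OTX-TP starts in this extension. A hyperemia grade that rose on OTX-TP in OTX-16-002 and persisted is thus outside the TEAE definition, and the by-visit table cannot identify it as a change. A shift table from the SAP baseline would show it.

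**IOP, for contrast.** Assume 200 eyes whose IOP changes are drawn with mean −4 and SD 3 mmHg (simulated), then set six eyes to a rise of 12 mmHg.

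| Statistic of change (mmHg) | Without the six rises | With them |
|---|---|---|
| Mean | −4.22 | −3.73 |
| Median | −3.99 | −3.97 |
| SD | 2.78 | 3.90 |
| Maximum | +4.6 | +12.0 |

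The mean and median barely move, but the planned SD and maximum do. The plan would show that a large rise occurred, not how many eyes had one.

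**The case against.** The strongest reply is that new local findings already have a planned route. Ocular TEAEs are the primary safety analysis, tabulated by preferred term, severity and relatedness. The protocol also lists the number of subjects needing rescue, and the SAP promises summaries of other safety outcomes. This stands in part, so a reader who infers that worsening cannot be seen at all goes too far. However, TEAEs depend on the investigator reporting a change in grade as an event, and the SAP gives no rule for that. Their window also excludes the earlier OTX-TP exposure. Rescue bears on IOP, is started at the investigator's discretion, and has no named analysis in the SAP. The promise of other summaries commits to nothing specific.

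A reader might also infer that IOP is reported only as means. The documents do not support this: change from baseline is stated, and it comes with SD, median, minimum and maximum. Nor does the protocol's 34 mmHg entry limit supply a measure of worsening. It is a level, and a rise of 10 mmHg reaches it only from a baseline of 24 or more.

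Three further objections are fair.

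- The ranges above are worst-case bounds on assumed inputs and shrink when findings are rare.
- Only hyperemia is described as graded, so worsening by a grade should not be asked of slit lamp or fundus findings.
- Shift tables do not recover eyes that leave the study. They only ensure that the same eyes are compared.

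**Conclusion.** The point holds for hyperemia, slit lamp/punctum, fundus and comfort. As written, the number of eyes worse than their own baseline on these measures would not be tabulated, although the plan provides within-eye change for IOP, visual acuity and OCT. Some cases would surface as TEAEs, but not worsening that began on OTX-TP in OTX-16-002.

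The practical size cannot be fixed from the documents. It ranges from 0 to 4 eyes at an assumed 2% prevalence to 0 to 60 eyes at 30%, and to 0 to 120 eyes for the assumed grade distribution, each out of 200. The conclusion assumes that these measures have usable values before first OTX-TP. The SAP supports this only indirectly, by naming OCT as the sole measure lacking data from OTX-16-002.

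For IOP the gap is minor: no count of eyes with a large rise. The sample-size statement and the primary safety analysis are unaffected. This is a free improvement, not a flaw that invalidates the plan.

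**What to change.** In the SAP's Safety Analyses section, keep the planned frequencies and add the following, using the baseline in Methods of Analyses and presenting by prior arm and overall:

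1. Shift tables from baseline to each visit and from baseline to the worst post-baseline value, by grade for hyperemia and by absent/present (or the category recorded) for slit lamp/punctum and fundus findings. Give the number and proportion of eyes, and of subjects counting either eye, that worsen or have a new finding. State which visits count towards the worst value, and use as denominator the eyes or subjects with both a baseline and a post-baseline value.
2. Change from baseline for ocular comfort.

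Optionally, add a count of eyes and subjects whose IOP rises from baseline by more than a prespecified amount. This would be a reporting category only, with no bearing on rescue.

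The cost is a few more tables from measures the trial already collects and a baseline the SAP already defines. Sample size, visits and hypotheses do not change.
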